8.1 Adverse events

8.1.1 Definitions and reporting

An adverse event is defined as the appearance of (or worsening of any pre-existing) undesirable sign(s), symptom(s), or medical condition(s) that occur after patient's signed informed consent has been obtained.

For patients whose MAPK pathway alteration(s) status is unknown and who sign the molecular pre-screening ICF, AEs which occur after signature of this consent will only be captured if they meet the definition of serious as outlined in [Section 8.2](#) and are reported to be causally related with study procedures (e.g. an invasive procedure such as biopsy). Once the main study ICF is signed, all AEs per the descriptions below will be captured in the Adverse Event eCRF.

Patients for whom the MAPK pathway alteration(s) status is known, and confers eligibility to the study, will sign the main study ICF only. All AEs per the descriptions below will be captured in the Adverse Event eCRF.

Abnormal laboratory values or test results occurring after informed consent constitute adverse events only if they induce clinical signs or symptoms, are considered clinically significant, require therapy (e.g., hematologic abnormality that requires transfusion or hematological stem cell support), or require changes in study medication(s).

Adverse events that begin or worsen after informed consent should be recorded in the Adverse Events eCRF. Conditions that were already present at the time of informed consent should be recorded in the Medical History page of the patient's eCRF. Adverse event monitoring should be continued for at least 30 days following the last dose of study treatment. Adverse events (including lab abnormalities that constitute AEs) should be described using a diagnosis whenever possible, rather than individual underlying signs and symptoms. When a clear diagnosis cannot be identified, each sign or symptom should be reported as a separate Adverse Event.

Adverse events will be assessed according to the Common Terminology Criteria for Adverse Events (CTCAE) version 4.03, unless otherwise stated.

If CTCAE grading does not exist for an adverse event, the severity of mild, moderate, severe, and life-threatening, corresponding to Grades 1 - 4, will be used. CTCAE Grade 5 (death) will not be used in this study (but is collected as a seriousness criterion); rather, information about deaths will be collected through a Death form.

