The occurrence of adverse events should be sought by non-directive questioning of the patient (subject) during the screening process after signing informed consent and at each visit during the study. Adverse events also may be detected when they are volunteered by the patient (subject) during the screening process or between visits, or through physical examination, laboratory test, or other assessments. As far as possible, each adverse event should be evaluated to determine:

- The severity grade (CTCAE Grade 1-4)
- Its duration (Start and end dates) or Ongoing after the 30 Day safety follow-up
- Its relationship to the study treatment (Reasonable possibility that AE is related: No, Yes)
- Action taken with respect to study or investigational treatment (none, dose adjusted, temporarily interrupted, permanently discontinued, unknown, not applicable)
- Whether medication or therapy was given (no concomitant medication/non-drug therapy, concomitant medication/non-drug therapy)
- Outcome (not recovered/not resolved, recovered/resolved, recovering/resolving, recovered/resolved with sequelae, fatal, unknown)
- Whether it is serious, where a SAE is defined as in [Section 8.2.1](#) and which seriousness criteria have been met.

All adverse events should be treated appropriately. If a concomitant medication or non-drug therapy is given, this action should be recorded on the Adverse Event eCRF.

Once an adverse event is detected, it should be followed until its resolution or until it is judged to be permanent, and assessment should be made at each visit (or more frequently, if necessary) of any changes in severity, the suspected relationship to the study treatment, the interventions required to treat it, and the outcome.

Progression of malignancy (including fatal outcomes), if documented by use of appropriate method (for example, as per RECIST criteria for solid tumors), should not be reported as a serious adverse event.

Adverse events separate from the progression of malignancy (example, deep vein thrombosis at the time of progression or hemoptysis concurrent with finding of disease progression) will be reported as per usual guidelines used for such events with proper attribution regarding relatedness to the drug.

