2.11 Analysis of safety variables

The assessment of safety is based on the type and frequency of Adverse Events (AEs) as well as on the number of laboratory values that fall outside of pre-determined ranges (Common Toxicity Criteria for Adverse Events (CTCAE version 4.03) grading limits or normal ranges as appropriate). Other safety data include ECOG performance status, electrocardiogram and vital signs.

The Safety set will be used for summaries and listings of safety data with the exception of dose limiting toxicities (DLTs) for which the DDS will be used.

The overall observation period will be divided into three mutually exclusive segments:

- 1. Pre-treatment period: from day of patient's informed consent to the day before first dose of LTT462,
- 2. On-treatment period: from day of first dose of LTT462 to 30 days after last dose of study medication,
- 3. Post-treatment period: starting at Day 31 after last dose of LTT462.

Safety summary tables described in the following sections will include assessments collected during the treatment period, unless otherwise stated.

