2.11.1 Adverse events

Data handling

AEs will be coded and graded using the latest version of MedDRA and CTCAE, respectively, available at the time of reporting. If CTCAE grading does not exist for an AE, grades 1, 2, 3, or 4 corresponding to the severity of mild, moderate, severe, and life-threatening, respectively, will be used. CTCAE grade 5 (death) will not be used in this study. Death information will be collected during treatment, safety follow up, and post-treatment follow up.

Progression of malignancy (including fatal outcomes), if documented by use of appropriate method (for example, as per RECIST criteria for solid tumors, should not be reported as a serious adverse event.

Adverse events separate from the progression of malignancy (example, deep vein thrombosis at the time of progression or hemoptysis concurrent with finding of disease progression) will be reported as per usual guidelines used for such events with proper attribution regarding relatedness to the drug.

A patient with multiple CTCAE grades for an AE will be summarized under the maximum grade recorded for the event. A subject with multiple occurrences of an AE is counted only once in the AE category (e.g. SOC, preferred term).

The incidence of a given AE is defined as the ratio of total number of patients experiencing the given AE at least once (defined by its preferred term [PT]) divided by the total number of patients at risk (i.e. part of the safety set). The incidence of AEs will be performed on treatment-emergent events only, i.e., AE that first occurs or worsens during treatment up to 30 days following the last treatment administration. The listing of adverse events will include all events reported during the study conduct.

Reports

The following AE summaries will be produced, including maximum CTC grade 3/4, in addition to the primary analyses:

- AEs regardless of study drug relationship
- AEs suspected to be study drug related
- AEs leading to discontinuation of study drug, regardless of study drug relationship
- AEs which are not SAEs regardless of study drug relationship
- All SAEs regardless of study drug relationship
- On-treatment deaths with cause of death by preferred term
- All deaths, with cause of death by primary system organ class and preferred term

A missing AE start date will be imputed using the following logic matrix described below.

Novartis	Confidential	Page 17
SAP	13-May-2019 (11:03)	CLTT462X2101

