Table 2-3	Imputation rules for a partially missing AE start date

	AEM MISSING	AEM < TRTM	AEM = TRTM	AEM > TRTM
AEY MISSING	No imputation	No imputation	No imputation	No imputation
AEY < TRTY	(D)	(C)	(C)	(C)
AEY = TRTY	(B)	(C)	(B)	(A)
AEY > TRTY	(E)	(A)	(A)	(A)

AEM: Month AE started; AEY: Year AE started

TRTM: Month treatment started; TRTY: Year treatment started

Table 2-2 is the legend to the logic matrix shown in Table 2-1 and details the relationship of AE start date to study treatment start date.

 Table 2-4
 Imputation legend and AE/treatment start date relationship

	AE start date relationship	Imputation
(A)	After treatment start or Uncertain	MAX(01MONYYYY, TRTSTD+1)
(B)	Uncertain	TRTSTD+1
(C)	Before treatment start	15MONYYYY
(D)	Before treatment start	01JULYYYY
(E)	After treatment start	01JANYYYY

Before treatment start: Partial date indicates AE start date is prior to treatment start date. After treatment start: Partial date indicates AE start date is after treatment start date.

Uncertain: Partial date insufficient to determine relationship of AE start date to treatment start date.

No imputation will be performed for AE end dates.

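### SAP Tables 2-3 and 2-4, cell (B): a partial AE start date is set to the day after first dose without looking at the end date, so an AE known to have ended before treatment is counted as treatment-emergent

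*SAP*

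**What the plan says.** - **The imputation rule (SAP 2.11.1, Tables 2-3 and 2-4).** The inputs are the AE month and year, the treatment-start month and year, and the treatment start date (TRTSTD). Cell (B) covers an AE in the treatment-start year whose month is missing or equals the treatment-start month, and it assigns TRTSTD+1. Its label is explained as "Uncertain: Partial date insufficient to determine relationship of AE start date to treatment start date".
- **The end date.** In this rule it appears only in the statement "No imputation will be performed for AE end dates". SAP 6.2 deals with end dates that are missing or fall after the cut-off. It has no check of start against end.
- **What is counted (SAP 2.11.1).** "The incidence of AEs will be performed on treatment-emergent events only, i.e., AE that first occurs or worsens during treatment", extended to 30 days after the last dose. SAP 2.11 sets the window: "On-treatment period: from day of first dose of LTT462 to 30 days after last dose of study medication". The pre-treatment period is a separate, non-overlapping segment.
- **What is collected (Protocol 8.1.1).** "Adverse events that begin or worsen after informed consent should be recorded in the Adverse Events eCRF". Among the items sought for each event is "Its duration (Start and end dates) or Ongoing after the 30 Day safety follow-up".

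**The concern.** Treating an undetermined onset as on-treatment is an ordinary conservative convention and is not in dispute. The difficulty is that cell (B) decides what is undetermined from the partial start date alone. A complete end date before first dose settles the question, because an event that is already over cannot first occur or worsen during treatment. Applying TRTSTD+1 to it contradicts the recorded end date and the SAP's definition of a treatment-emergent event. It also moves the event across the boundary between the pre-treatment and on-treatment periods.

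AE incidence is a primary safety endpoint (SAP 2.9.1), and its tables are restricted to treatment-emergent events, so the imputed start date decides whether such an event is reported there. At stake are start dates later than end dates in the data, and some over-counting in the tables that include AEs regardless of relationship to study drug.

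**Working it through.** The plan gives no figure to reproduce. The check applies Tables 2-3 and 2-4 as written.

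**1. One worked case (illustrative dates).**
- First dose 20 June 2018; AE start recorded as June 2018 with the day missing; AE end 12 June 2018.
- Year equal and month equal, so cell (B) applies: imputed start = TRTSTD+1 = 21 June 2018.
- 21 − 12 = 9 days, so the start is 9 days after the recorded end.
- 21 June lies between first dose and last dose + 30 days, so the event is counted as treatment-emergent.

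TRTSTD+1 falls inside the on-treatment window for every treated patient, so the same happens whenever cell (B) meets an end date before first dose.

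**2. How often cell (B) is reached, given such a record.** Take every first-dose date in a 365-day year and every AE that starts and ends on days −14 to −1. The 14 days are the screening window in Protocol 7.1. Each possible start and end pair has equal weight.
- Pairs per first-dose date: 1 + 2 + … + 14 = 105. Total: 365 × 105 = 38,325.
- *Day missing.* Cell (B) needs the true start to lie in the calendar month of first dose. First doses on days 1 to 15 of a month contribute 0 + 1 + 3 + … + 105 = 560 pairs per month. Later first-dose dates contribute all 105 pairs. Total: 12 × 560 + (365 − 12 × 15) × 105 = 6,720 + 19,425 = 26,145, and 26,145 / 38,325 = 68%.
- *Day and month missing.* Cell (B) needs only the same year, so only first doses on 1 to 15 January lose pairs. Total: 560 + 350 × 105 = 37,310, and 37,310 / 38,325 = 97%.
- In all these cases the imputed start is after the known end. The remaining cases fall in cells (C) or (D) and stay pre-treatment.

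These shares are conditional on an AE having a partial start date and a complete end date before first dose. They do not estimate how often that combination occurs in the trial.

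**3. The other cells.**
- Cell (A) applies only when the AE month is later than the treatment-start month, or the AE year is later with the month known. The first of that month is then already at or after TRTSTD+1, so the rule returns the first of the month, which cannot exceed a valid end date.
- Cell (E) returns 1 January of a later year and is equally safe.
- Cell (C) may put the 15th after a known end date, but the event stays pre-treatment and its classification does not change.

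Only cell (B) misclassifies.

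**4. With a cap at a known end date.** Every enumerated AE ends on day −1 or earlier. A start no later than that end is pre-treatment, so none of the 38,325 cases is counted as treatment-emergent and none starts after it ends. An AE that ends on the day of first dose would start that day and stay on-treatment. With a missing, partial or later end date, TRTSTD+1 is unchanged.

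**The case against.** **A check may exist elsewhere.** SAP section 1 places derived-variable specifications in a programming document that is not available here. That lowers certainty. But the SAP sets out this rule in full without referring to that document for it, and a programmer who follows the tables literally produces the impossible record.

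**Such records may be rare or absent.** Protocol 9.4 provides for queries on discrepancies and missing values, which should reduce partial dates. The documents show that pre-treatment AEs are collected and that both dates are sought. They do not show that any AE combines a partial start with a complete pre-dose end. This stands, and it limits the size of the point.

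**The reach is narrow.** A DLT must be an event whose relationship to LTT462 cannot be ruled out, arising in the first 28 days of treatment (Protocol 6.2.4). The table of drug-related AEs rests on recorded attribution. An event known to be over before dosing should enter neither. A reader might infer that the DLT model or dose decisions are distorted; the documents do not support that.

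**Large shifts in incidence.** A reader might take the 1 to 6 patients of Protocol 6.2.3.2 as the table denominator and infer that one event moves an incidence by 17 to 100 percentage points. That range is the cohort size. The tables are by treatment group, which pools cohorts with the same dose and regimen (Protocol 10; SAP 2.1). A patient is also counted once per preferred term, so a misdated event changes nothing for that term if the patient has it again on treatment.

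**Concomitant medications.** SAP 2.8.2 reuses the AE start-date rule, but therapies starting before or after treatment start all go to one listing. No summary depends on the imputed date.

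**Conclusion.** The rule is wrong as written, with low severity. In cell (B), an AE with a complete end date before first dose receives a start after its end and enters the all-causality treatment-emergent tables, contrary to the SAP's definition of those events. This is more than a missing detail, because the stated rule gives a definite wrong answer when the recorded data already give the right one.

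The number of affected AEs cannot be derived from the documents and is probably small. The direction is over-counting, which is conservative for a safety endpoint. If one patient is wrongly counted for a term in a group of N, that incidence rises by 100/N points. With 6 patients, the minimum at the dose selected for expansion, this is 100/6 = 16.7 points; with 8, the example in Protocol 6.2.3.2, it is 100/8 = 12.5. The documents do not fix the group sizes, so these figures are illustrations.

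The conclusion assumes that Tables 2-3 and 2-4 are programmed as they stand. It does not extend to cell (A), or to cell (B) where the end date is missing, partial or after first dose.

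**What to change.** Add one sentence to SAP Table 2-4: *If a complete AE end date is available and is earlier than the imputed start date, the imputed start date is set to the AE end date.* An AE that ended before first dose is then classed as pre-treatment, and the conservative TRTSTD+1 remains where timing is truly uncertain. The same cap may be applied to concomitant medication start dates in SAP 2.8.2, for consistency of the listing only.

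The cost is one SAP sentence and one programming condition, with no new data. Under SAP section 1 the change is made by amendment before database lock, or by addendum after it. If the programming specification already contains such a check, stating it in the SAP is enough.

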2.11.2 Laboratory data

Data handling

All laboratory values will be converted into SI units, as appropriate, and the severity grade calculated using Common Terminology Criteria for Adverse Events (CTCAE), version 4.03. For laboratory tests where grades are not defined by CTCAE, results will be graded by the low/normal/high classifications based on local laboratory normal ranges.

Laboratory parameters with CTCAE grading will follow the EASE Lab CTC grade derivations:

• Lab values will be analyzed using programmable numeric CTCAE criteria, therefore not considering clinical components (e.g., life-threatening consequences). It is therefore understood that AEs on lab toxicities might not correspond fully with lab toxicities on lab values

The new Novartis Oncology standard definitions of lab CTC grades (including direction of severity) are given in Appendix 6.3. Of note this is the current version of the EASE report, at the time of the CSR, the most updated version will be applied,

Novartis	Confidential	Page 18
SAP	13-May-2019 (11:03)	CLTT462X2101

Data analysis

A listing of patients with abnormal laboratory values of CTCAE grade 3 or 4will be produced for the hematology and chemistry laboratory data.

2.11.3 Other safety data

2.11.3.1 Electrocardiograms

Data handling

- Unscheduled ECGs are included in the analysis of notable value.
- Triplicate 12 lead sequential readings will be performed at baseline and post-baseline for a patient at the given time points, refer to section 7.2.2.6.1 of the study protocol, all individual values are transferred, in which case, ECGs are averaged over the patient and then across patients for change from baseline analysis.
- No adjustment (in the variance) is made to account for different patients having differing number of ECGs being averaged at a given time point. (It is assumed that the scheduled assessments for each patient are the same and any deviations are sporadic and minor.)

Data Analysis

A listing of ECG intervals will be presented, by treatment group for the dose escalation part.

2.11.3.2 Vital signs

A listing of patients with abnormal vital signs will be provided.

2.12 Tolerability

Tolerability of study drug treatment will be assessed by summarizing the number and percentage of dose interruptions and dose reductions per patient, together with reasons for dose interruption and dose reductions. Dose intensity and relative dose intensity of LTT462 per patient will be summarized. For relative dose intensity, the number and proportion of patients

Novartis	Confidential	Page 20
SAP	13-May-2019 (11:03)	CLTT462X2101

within the following categories will be presented: $< 0.5, \ge 0.5 - < 0.75, \ge 0.75 - < 0.9, \ge 0.9 - < 1.1$ and ≥ 1.1 .

2.13 Pharmacokinetic data

Pharmacokinetic parameters will be determined by non-compartmental method(s) using the pharmacokinetic profile of LTT462. PK parameters listed below will be derived and reported, when feasible.

AUClast The AUC from time zero to the last measurable concentration sampling time (tlast) (mass x time x volume-1) AUCtau The AUC calculated to the end of a dosing interval (tau) at steady-state (amount x time x volume-1) AUCinf The AUC from time zero to infinity (mass x time x volume-1) The maximum (peak) observed plasma, blood, serum, or other body fluid drug Cmax concentration after single dose administration (mass x volume-1) The time to reach maximum (peak) plasma, blood, serum, or other body fluid drug Tmax concentration after single dose administration (time) Observed concentration at the end of a dosing interval (taken directly before next Cmin administration) CL/F The total body clearance of drug from the plasma (volume x time-1) Racc Accumulation ratio calculated using AUCtau at steady state divided by AUCtau at Day 1 T1/2 Effective elimination half-life

 Table 2-8
 Non-compartmental pharmacokinetic parameters

2.13.1 Data handling principles

All concentrations below the lower limit of quantitation (LLOQ) or missing data will be labeled as such in the concentration data listings. Concentrations below the LLOQ will be treated as zero in summary statistics and for the calculation of pharmacokinetic parameters, unless otherwise stated under the Pharmacokinetic Analysis Set.

At the time of analysis, concentration data from patients may be removed from the estimation of certain PK parameters depending on the number of available blood samples, concomitant medications, vomiting, etc. Specific time points might be removed from the analysis, if technical issues with the sample are reported (e.g. sampling issues, missing information). These patients and concentration data points will be identified at the time of analysis.

2.13.2 Data analysis set

All pharmacokinetic data analyses and PK summary statistics will be based on PAS. Only PK blood samples with date and time and for which the last prior dose dates and times are adequately recorded will be included in the PK analyses.

2.13.3 Basic tables, figures, and listing

Descriptive statistics will be presented for all pharmacokinetic parameters, as described below.

Table 2-9	Descriptive analysis
-----------	----------------------

Parameters	Descriptive statistics	
$AUC^{(1)}$, C_{min} , C_{max} , CL/F , accumulation ratio R_{acc} , $T_{1/2}$	Mean standard deviation, CV% mean, geometric mean, CV% geo-mean, median, minimum, and maximum. 90% CI for R _{acc.}	
T _{max}	Median, minimum, and maximum.	
<other parameters=""> None</other>		
 ⁽¹⁾ Includes AUC_{inf}, AUC_{tau}, AUC_{last} (or all AUC parameters) CV% = coefficient of variation (%) = sd/mean*100 CV% geo-mean = sqrt (exp (variance for log transformed data)-1)*100 		

Zero concentrations will not be included in the geometric mean calculations. Tmax will be summarized in terms of median values and ranges. Missing concentrations or PK parameter values will not be imputed. A listing of derived PK parameters per patient will be produced by treatment group.

Arithmetic and geometric mean plasma concentration versus time profile plots will be generated for LTT462. Further graphical exploratory analyses (such as individual plasma concentration versus time) will be carried out if deemed appropriate.

